## 3 Study Design and Methods

### 3.1 Overall Study Design

The Probiotics trial has a parallel group design with a placebo control. We will not describe specifics about the active agent or placebo here, as these are contained in the protocol. We will refer to the two trial arms as Active and Placebo. Study participants will be randomized to Active or Placebo, each having equal allocation. Treatment with the assigned therapy is to commence immediately following randomization. The primary analysis will be performed on an intention-to-treat basis. We will also use an enrichment design, possibly modifying the eligibility criteria of the trial based on interim results.

### 3.2 Randomization and Blinding

#### 3.2.1 Method of Treatment Assignment

Randomization will be balanced among the study arms. Randomization will be stratified by clinical center and by duration of symptoms. Permuted blocks of lengths 2, 4, and 6 will be used for randomization. This trial will use a web-based system for randomization provided by randomize.net. Randomization/kit numbers will be provided in a scrambled order and separated into arms (A and B).

**Delivery of Randomization** Randomizations will be delivered to the clinical centers using a web-based system administered by randomize.net. This system will use each enrolled patient's clinical center and duration of symptoms (<48 hours vs. 48 hours or more) to deliver the next assigned treatment.

In this trial, there will be no "emergency backup" randomization, as we expect to be able to capture a sufficient number of patients.

#### 3.2.2 Blinding

The Probiotics trial will be performed in a double-blind fashion. All study personnel, including investigators and research coordinators, shall be blinded to assigned treatment arm for each enrolled subject. Of necessity, biostatisticians involved in presenting interim analyses

to the DSMB will be aware which subjects have received “Treatment A” and which have received “Treatment B”, but they will not be aware of the identity of the two arms.

Unblinded personnel in this study will include: the central research pharmacist and, possibly, a pharmacy monitor contracted by the DCC expressly for the purpose of ensuring assigned treatments have been correctly prepared and delivered in this study. The DSMB may request to be unblinded to treatment assignment at any time.

### 3.3 Sample Size and Power Determination

The primary outcome is binary: whether total post-enrollment Modified Vesikari Score (MVS) is  $\geq 9$  during the 2-week follow-up period. The difference between arms will be tested at a 0.05 level. The null and alternative hypotheses are, respectively,

$$H_0 : p_A = p_P \quad \text{and} \quad H_1 : p_A \neq p_P,$$

where  $p_A$  and  $p_P$  are, respectively, the true probabilities of  $MVS \geq 9$  on the Active drug and on Placebo.

Our pilot data indicate that 25% of patients will have moderate to severe disease ( $MVS \geq 9$ ) during the course of their illness. Furthermore, expert surveys indicated that an absolute risk reduction of 10% would constitute a minimal clinically-important difference (MCID). Therefore, our sample size calculation assumed a 25% event rate in the control group for which we desire to detect an absolute beneficial treatment effect of 10% with 90% power (0.1 Type II error rate). Using a two-sided type I error ( $\alpha$ ) of 0.05 and the hypothesized proportions yields a required total sample size of 670 patients. Our expected power, should we find different event rates in our 2 groups, is displayed in the following table.

Placebo	Active	% Difference	Power
0.30	0.21	9%	0.76
0.30	0.20	10%	0.85
0.25	0.15	10%	0.90
0.25	0.16	9%	0.82
0.25	0.17	8%	0.72
0.20	0.10	10%	0.95
0.20	0.12	8%	0.81
0.20	0.13	7%	0.69

Based on previous work by our group, we assumed 10% loss to follow-up ( $670/0.90 = 744$ ), 5% drop-out, and 3% drop-in (caregivers who buy a probiotic agent to administer to their child) rate ( $744/(0.92)^2 = 879$ ). Adjustment for O’Brien-Fleming monitoring boundaries requires a further 2% increase. Thus, the total number randomized (final target sample size) will be 900.

## 4 Study Subjects and Analysis Populations

### 4.1 Analysis Populations

#### 4.1.1 Screening Population

The screening population (SCREEN) includes all patients who are screened for eligibility into the trial, regardless of randomization into the trial or treatment status. This population represents all patients who meet inclusion criteria outlined in the study protocol and who are screened in real-time by study staff at the site. This population will be used for reporting of study flow per CONSORT guidelines.

#### 4.1.2 Intention-to-Treat Population

The Intention-to-Treat (ITT) population includes all subjects who are randomized into the trial, regardless of adherence to the protocol, including, for example, subjects who receive no study drug. The ITT population will be used for the primary efficacy analyses in the study, as well as for main efficacy analyses of secondary and tertiary outcomes. All analyses using the ITT population will be based on each subject's assigned treatment arm, regardless of treatment actually received.

#### 4.1.3 Per-Protocol Efficacy Population

The Per-Protocol (PP) efficacy population includes all subjects in the ITT population who are verified to meet all study inclusion and exclusion criteria, who receive study drug according to their assigned study arm (defined as  $\geq 7$  out of 10 doses). This population will be used to examine whether results seen in the ITT population are maintained in the population adhering to the protocol.

#### 4.1.4 Safety Population

The safety population (SAFETY) includes all subjects who receive any study drug. Reporting of results based on this population will be summarized according to treatment received. This population will be used for analysis of adverse events and (in addition to ITT) to examine safety outcomes.

### 4.2 Study Subjects

#### 4.2.1 Inclusion and Exclusion Criteria

To be included in the study, patients:

- are between 3 and 48 months of age; AND

- have had 3 or more watery stools within 24 hours prior to screening; AND
- have had vomiting or diarrhea less than 7 days; AND
- have symptoms consistent with acute intestinal infectious process.

The following patients will be excluded from the study:

- patients with an indwelling vascular access line; OR
- patients with structural heart disease excluding non-pathological heart murmurs; OR
- patients receiving immunosuppressive therapy or having history of immunodeficiency; OR
- patients with hematochezia in the preceding 48 hours; OR
- patients with chronic gastrointestinal problems (e.g., short gut syndrome, inflammatory bowel disease); OR
- patients with known pancreatitis; OR
- critically ill patients; OR
- patients having a family member with an indwelling vascular access line, or on immunosuppressive therapy, or with a known immunodeficiency; OR
- patients with bilious emesis; OR
- patients who have used probiotics (supplement) in the preceding 2 weeks; OR
- patients previously enrolled in this trial; OR
- patients who are allergic to lactobacillus or Microcrystalline Cellulose (MCC); OR
- patients who are allergic to erythromycin, clindamycin, AND  $\beta$ -lactam antibiotics (all); OR
- patients who will not be available for daily follow-up while symptomatic; OR
- patients whose parent/guardian do not speak English or Spanish; OR
- patients under 6 months of age AND premature (<37 weeks).

### 4.3 Enrichment Design

The study design and power analysis described are based on the assumption of homogeneous treatment effect. We may also incorporate an enrichment design to restore the statistical power in case the presence of a subpopulation with a substantially low treatment effect is identified [1]. We are particularly interested in two potential subpopulations: participants with <48 hours of symptoms prior to presentation and those with 48 hours or more of symptoms. Based on pilot data, each subpopulation accounts for approximately 50% of the total population. The decision for enrollment modification will be made at the first interim analysis for efficacy. Specifically, three Mantel-Haenszel z-statistics will be calculated to compare the primary efficacy outcome between Active and Placebo groups for subjects in the total population and the two subpopulations, respectively. Denote these z-statistics as  $Z_{0,1}$ ,  $Z_{<48,1}$ , and  $Z_{>48,1}$ . Note that a positive z-statistic sign will be used to indicate superiority of probiotic relative to placebo.

First,  $Z_{0,1}$  will be compared to the O'Brien-Fleming boundary to determine whether the trial should be discontinued for efficacy (as described in Section 6.2). If the boundary is not crossed, or if the DSMB will otherwise recommend continuation of the trial, all three z-statistics will be considered. If  $Z_{0,1}$  is larger than both  $Z_{<48,1}$  and  $Z_{>48,1}$ , or if both  $Z_{<48,1}$  and  $Z_{>48,1}$  are  $>0.3$ , accrual will continue as before. Otherwise, future patients will be recruited only from the subpopulation with the larger z-statistic. All subjects, regardless of symptom duration will be included in the final analyses. At the second interim analysis and the final analysis (or any additional unplanned interim analysis), the following method will be used to test for efficacy.

Let  $Z_2$  be the Mantel-Haenszel z-statistic that is based only on subjects enrolled since the first interim analysis. Then, the final test statistic to be used is a weighted sum of the statistics from each stage:

$$Z = \left( \frac{n_1}{n_1 + n_2} \right) Z_{0,1} + \left( \frac{n_2}{n_1 + n_2} \right) Z_2,$$

where  $n_1$  and  $n_2$  are, respectively, the number of subjects enrolled prior to and following the first interim analysis. Note that, if no enrichment is performed (i.e., accrual from the full population),  $Z$  is asymptotically equivalent to the usual z-statistic ignoring the stages. This final  $Z$  value will be compared to the quantiles of the standard normal distribution corresponding to the interim or final boundaries described in Section 6.2. A significant result will indicate efficacy in the population that was enrolled following the first interim analysis.

Simulations were performed to evaluate the performance of this design. Additional assumptions/considerations:

- The (untreated) outcome rate in the subpopulation with greater than 2 days of symptoms is 20%, while it is 30% in the other subpopulation.

- Each subpopulation accounts for 50% of the overall population.
- The normal approximation to the binomial distribution was used, rather than a chi-square or Mantel-Haenszel test.
- The interim analyses occur at 35% and 70% of target patient enrollment.

Several different treatment effect scenarios were simulated. The results show that the enrichment design will increase power when the treatment effect differs by subpopulation, but will have little impact on power if the treatment effect is the same in both subpopulations. One slight disadvantage is that, depending on outcome rates, the enrichment design will only accrue a subpopulation after the first interim analysis with probability 0.05–0.35 when, in fact, there is a homogeneous treatment effect.

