## 8.2 Frequency of Interim Analysis:

The Data Safety Monitoring Board (DSMB) will meet after 80 patients (safety end points for 1 month), approximately 350 patients (end of 2nd year of enrollment) and 620 patients (end of 3rd year of enrollment) to review enrollment, study procedures, loss to follow-up, drop-in rate, and interim safety and efficacy results. The analyses will test the hypothesis that the probability of developing moderate-to-severe acute gastroenteritis in the probiotic arm is equal to that in the placebo arm. An analysis will also be conducted after 20 subjects under 6 months of age have been enrolled. The DSMB is to review interim data and make recommendations regarding continuation or modification of the study based on safety in this age group. Conservative O'Brien-Fleming monitoring boundaries, implemented using the Lan-DeMets  $\alpha$ -spending function approach, will be used as guidelines for early stopping for efficacy.

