#### **8.3.5 Monitoring Serious Adverse Events**

The Principal Investigator of the Data Coordinating Center ([name]) will act as the medical monitor for this study. If [name] is unavailable, a qualified physician will be designated to fulfill this function. Site investigators and/or research coordinators will report serious adverse events to the Data Coordinating Center within 24 hours. A detailed completed report will be required to be sent to the Data Coordinating Center within 3 working days of the event, and the medical monitor will assess all serious adverse events reported from site investigators.

For each of these serious adverse events, the site investigator will provide sufficient medical history and clinical details for a safety assessment to be made with regard to continuation of the trial. The medical monitor will sign each SAE report after review. All SAE reports will be retained at the Data Coordinating Center, and all SAE reports will be available for review by DSMB members and NICHD staff.

In the unlikely event that the medical monitor believes an unexpected and study-related SAE warrants emergent cessation of enrollment in the trial, NICHD staff and the

DSMB chairperson will be immediately consulted. If these individuals concur with the judgment of the medical monitor, or if the NICHD staff and the DSMB chairperson cannot be reached expeditiously, the Data Coordinating Center will notify the study investigator ([name]) and all site investigators to cease enrollment in the trial. Resumption of enrollment will not occur without consent of the NICHD staff after discussion with the DSMB.

In accordance with local IRB requirements, the site investigator may be required to report such events to the IRB in addition to notifying the Data Coordinating Center.

After notification of the NICHD Program Official or Project Officer, and the DSMB chairperson, of *serious, unexpected, and study-related* adverse events or unanticipated problems (UP), decisions will be made whether to continue the study without change, and whether to convene the entire DSMB for an emergent meeting. If a decision is made to suspend enrollment in the trial, this will be reported to the study investigator ([name]) and all clinical investigators, who will be instructed to report this to their local IRB.

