## 6 Overview of Planned Analyses

### 6.1 Schedule of Interim Analyses

This study has two planned *formal* interim analyses. There will be additional meetings for review of the protocol, safety of the first 80 patients, and other meetings, as necessary. Formal interim analyses will examine treatment efficacy as well as patient safety. These analyses will be reviewed by the DSMB. The DSMB will, at their discretion, be able to request analyses additional to those described in this SAP.

The total target enrollment for this study is 900 subjects. We estimate that this will take 4 years. The first analysis (safety) will take place after enrollment of 80 subjects (40 of these  $<1$  year old and  $40 \geq 1$ ). The first formal efficacy interim analysis will take place after the second year of enrollment, after approximately 350 subjects have been enrolled. The second formal efficacy interim analysis will be performed after approximately 620 subjects have been enrolled. The DSMB is to review interim data and make recommendations regarding continuation or modification of the study.

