### 6.2 Stopping Rules for Interim Analyses

Two-sided O'Brien-Fleming boundaries, implemented using the alpha-spending function approach will be used. Specifically, if the analyses are performed exactly when planned, the significance levels that will be used at interim analyses are 0.00065 and 0.0136. If the trial reaches the anticipated total sample size, a significance level of 0.0457 will be used for the final test. These boundaries assure that the total Type I error rate will be less than or equal to 0.05.

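### SAP 4.3 has no branch for two negative subgroup z-statistics, and no action is written for a negative crossing of the two-sided boundary

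*Combined protocol and SAP*

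**What the plan says.** **Enrichment rule.** SAP v1.2, 4.3 computes three Mantel-Haenszel z-statistics at the first efficacy look: overall (Z0,1), under 48 hours of symptoms, and 48 hours or more. Positive means probiotic is better. Z0,1 is first compared with the O'Brien-Fleming boundary "to determine whether the trial should be discontinued for efficacy". If it does not cross, or the DSMB recommends going on regardless, accrual is unchanged when Z0,1 is larger than both subgroup values or when both subgroup values exceed 0.3. "Otherwise, future patients will be recruited only from the subpopulation with the larger z-statistic".

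**Protocol version of the same rule.** Protocol V3.0, 5.3.1 drops a subgroup only if its z is below 0.3 and also below the total-population z.

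**Boundary.** SAP 6.2: "Two-sided O'Brien-Fleming boundaries, implemented using the alpha-spending function approach will be used", and "the significance levels that will be used at interim analyses are 0.00065 and 0.0136", with 0.0457 at the end. Protocol 8.2 says the boundaries "will be used as guidelines for early stopping for efficacy".

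**Other oversight.** SAP 6.1: "The DSMB is to review interim data and make recommendations regarding continuation or modification of the study". Protocol 8.3.5 gives a separate route, starting "In the unlikely event that the medical monitor believes an unexpected and study-related SAE warrants emergent cessation of enrollment in the trial".

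**The concern.** Enrichment is justified in SAP 4.3 as a way to restore power when one subgroup has a substantially low treatment effect. That reasoning needs the other subgroup to be doing better on probiotic. When both are doing worse there is nothing to enrich for, yet the rule has no floor and still picks one of them. Followed as written, later recruitment is limited to about half the eligible population, in a subgroup whose own interim result is unfavourable. About 620 − 350 = 270 children would be recruited on that basis before the second look.

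The boundary raises a related question. A two-sided boundary has a lower limb, but a DSMB reading the protocol and SAP would find no statement of what follows if that limb is crossed.

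**Working it through.** **1. Reproduce the plan's boundary.** Inputs: looks at 350, 620 and 900 (SAP 6.1) and overall two-sided alpha 0.05 (SAP 3.3). O'Brien-Fleming-type spending with 0.025 in each tail is 4[1 − Φ(2.241/√t)]. At t = 350/900 = 0.389 this is 4[1 − Φ(3.594)] = 0.00065. Numerical recursion for the later looks gives 0.01363 and 0.04572. All three match SAP 6.2. Spending 2[1 − Φ(1.96/√t)] gives 0.00167 at the first look and the classical O'Brien-Fleming design gives 0.00127; neither matches. The stated levels therefore correspond to z = ±3.41, ±2.47 and ±2.00, and a lower limb exists.

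**2. Show that two negative z's always fall through.** Write Z0,1 = w1·Z1 + w2·Z2 with wi = √(Vi/(V1+V2)), where Vi is the Mantel-Haenszel variance in subgroup i. Then w1² + w2² = 1, so w1 + w2 > 1. If Z1 and Z2 are both negative,

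Z0,1 ≤ (w1 + w2)·max(Z1, Z2) < max(Z1, Z2).

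Z0,1 therefore cannot exceed both, and neither exceeds 0.3. The restricting branch applies every time.

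**3. Example.** Take 88 children per arm per subgroup. U is placebo events minus their expectation.
- Under 48 hours, placebo 26 and active 31: U = 26 − 28.5 = −2.5, V = 9.69, z = −0.80.
- 48 hours or more, placebo 18 and active 22: U = 18 − 20 = −2.0, V = 7.77, z = −0.72.
- Overall: −4.5/√17.46 = −1.08.

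SAP 4.3 sends all later recruitment to the subgroup at −0.72. Under protocol 5.3.1 neither −0.80 nor −0.72 is below −1.08, so neither subgroup is dropped. The same data give two different enrolment decisions.

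**4. Frequency.** Inputs from SAP 4.3: control rates 30% and 20%, equal subgroups. First look at about 350 (SAP 6.1), simulated as 87 per arm per subgroup, 400,000 trials per row. The increases on active are assumptions; the documents give no harm estimate.

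| Increase in MVS ≥ 9 on active | Z0,1 below −3.41 | Both z's negative | Both negative, boundary not crossed | Of both-negative: protocol 5.3.1 drops neither |
|---|---|---|---|---|
| none | 0.03% | 22% | 22% | 58% |
| 5 points | 0.9% | 56% | 55% | 61% |
| 8 points | 3.8% | 74% | 71% | 65% |
| 10 points | 8.4% | 84% | 75% | 68% |

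SAP 4.3 restricted accrual in 100% of both-negative trials in every row. Under the 10-point benefit the trial is designed for, both z's are negative in about 0.1% of trials.

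**5. Uses of the boundary, side by side.** SAP 6.2 gives two-sided levels. SAP 4.3 and protocol 8.2, the places that say what the boundary is for, name efficacy only. Neither document attaches an action to z below −3.41 or −2.47.

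**The case against.** A reader might infer that nothing written responds to a worse outcome on probiotic, or that the SAP orders the trial to carry on through harm. The documents do not support either reading.

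- The boundary is two-sided, and its levels reproduce only with 0.025 in the unfavourable tail. What is missing is a consequence, not a limb.
- The DSMB reviews safety after 80 children, after 20 infants under 6 months, and at about 350 and 620 (protocol 8.2). It receives adverse events by arm (protocol 5.1), may request further analyses (SAP 6.1), may be unblinded at any time (SAP 6.3), and has a charter (protocol 8.1) that is not among these documents. The medical monitor's SAE route is also written.
- The enrichment rule decides whom to recruit if the trial continues; whether it continues is a matter for the DSMB. Enrichment is worded as optional in SAP 4.3, though as definite in SAP 3.1, and protocol 8.2 treats the boundaries as guidelines.
- Monitoring harm by judgment, without a numerical threshold, is a legitimate design. Two slightly negative z's, each from about 174 children, may be noise.

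All of this stands and limits the point. It does not supply the missing branch, remove the conflict between SAP 4.3 and protocol 5.3.1, or say what a negative crossing means. The medical monitor's route responds to an individual SAE and does not compare MVS ≥ 9 between arms.

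**Conclusion.** The concern holds in a limited form. Falling through to restriction when both z's are negative is an algebraic certainty and rests on no assumption about harm. Its frequency rests on the SAP's control rates, equal subgroups and a first look near 350: about 22% of trials with no effect, and about 55%, 71% and 75% under assumed harms of 5, 8 and 10 points. In about 58–68% of both-negative cases over that range, the protocol's rule drops neither subgroup while the SAP's restricts accrual. The boundary point is a gap in wording: a two-sided limit with only an efficacy use stated in the protocol and SAP. It should not be read as an absence of harm monitoring, nor as a case for a particular harm threshold.

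**What to change.** 1. In SAP 4.3, add: if both subgroup z-statistics are negative, the enrichment rule does not restrict accrual, and the result is passed to the existing DSMB at the review it already holds. Reconcile 4.3 with protocol 5.3.1 so that a single rule applies.
2. Reconcile SAP 6.2 with SAP 4.3 and protocol 8.2 by stating what a negative crossing of the two-sided boundary means. Any other harm threshold is for the sponsor and DSMB to decide.

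Cost: wording in the two documents, using the existing committee and analyses. The new branch offers no extra opportunity to declare efficacy, so it spends no efficacy alpha. It would apply in about 22% of trials when the drug has no effect, which is a frequent event and should be presented to the DSMB as such. It could also forgo a useful restriction when only one subgroup benefits, but seldom. With 30% falling to 20% in one subgroup and no effect in the other, the first z averages about 0.10/√(2 × 0.25 × 0.75/87) = 1.52. It is negative with probability about 0.064, and both are negative in roughly half of that, about 3%.

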## 5 Data Analysis

The hypotheses of this study are:

1. In children with acute gastroenteritis, probiotic administration in the emergency department will be associated with a clinically-important decrease in the proportion of children suffering from moderate-severe disease, defined by a validated Modified Vesikari Score  $\geq 9$ , compared to placebo.
2. In children with acute gastroenteritis, probiotic administration will not be associated with serious adverse events, and will have a similar rate of side effects (e.g. bloating, fever) as compared to placebo-treated children.

All analyses will be undertaken by the intention-to-treat (ITT) principle, except for adverse events, which will use the as-treated principle (compare the subjects based on the treatment regimen that they received). Patients who drop out or inadvertently crossover will be followed and included in the ITT analysis. All statistical tests of hypotheses will be two-sided. Baseline characteristics will be analyzed to determine if there is a need to adjust for differences between groups in exploratory analyses. Sensitivity analyses will be performed to assess the possibility and consequences of non-random loss to follow-up. The proportions of children experiencing an unscheduled healthcare visit or any potential adverse effect, as reported by the caregivers, will be compared between groups using the Mantel-Haenszel test, stratified by site. The analysis will evaluate the presence/absence of pre-specified side effects, as an aggregate outcome variable. A per-protocol analysis will be conducted to provide additional insight as non-compliance may result in an underestimation of the benefits of probiotics in the ITT analysis.

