This outcome will be tabulated by treatment for each stratum (clinical center and duration of symptoms). A Mantel-Haenszel statistic, assessing the effect of treatment on the primary outcome controlling for strata, will be calculated to test the primary hypothesis. Summary statistics for the effect sizes will be given. For dichotomous outcomes, Mantel-Haenszel risk ratios will be reported to the DSMB at interim analyses. Choice of final summary statistic reported (e.g., risk difference, risk ratio, or odds ratio) will be based, in part, by which statistic is least variable across subgroups (i.e., shows the smallest degree of interaction across subgroups).

It is expected that, for both the final analyses as well as interim analyses, the asymptotic version of the Mantel-Haenszel test will be appropriate. This analysis will be performed using SAS PROC FREQ. In the case of low outcome counts, which may occur within strata at early interim analyses, the Mantel-Fleiss criterion will be assessed. If the criterion has a value less than 5, the exact version of the Mantel-Haenszel test will be used and the two-sided p-value will be defined as the sum of all probabilities of test statistics with point probabilities less than or equal to that of the observed value.

In the event any patients were randomized within an incorrect stratum (i.e., wrong duration of symptoms) due to misspecification at time of randomization, the actual rather than assigned category will be used in the above analysis.

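### The stage-combined Z in SAP 4.3 is printed with weights n1/n and n2/n instead of their square roots; applied as written, power falls from 90% to about 68% and type I error to about 0.7%.

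*Combined protocol and SAP*

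**What the plan says.** SAP v1.2 section 4.3 states that, at the second interim, the final analysis and any unplanned interim, "the final test statistic to be used is a weighted sum of the statistics from each stage":

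Z = [n1/(n1+n2)] Z0,1 + [n2/(n1+n2)] Z2

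Here n1 and n2 are the numbers enrolled before and after the first efficacy interim, Z0,1 is the Mantel-Haenszel z at that interim, and Z2 is the Mantel-Haenszel z from later enrollees only. The rule is not conditional on enrichment having been triggered. The section says that without enrichment Z "is asymptotically equivalent to the usual z-statistic ignoring the stages", and that Z "will be compared to the quantiles of the standard normal distribution corresponding to the interim or final boundaries described in Section 6.2". SAP v1.1 section 4.3 prints the same formula.

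Section 7.2 describes the primary test differently: a stratified Mantel-Haenszel statistic "will be calculated to test the primary hypothesis", with no stage weights. Section 7.2.1, on pooling across imputed datasets, also ignores the stages and takes the standard error of z as 1.

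On operating characteristics, section 3.3 says "The difference between arms will be tested at a 0.05 level" and assumes a "25% event rate in the control group for which we desire to detect an absolute beneficial treatment effect of 10% with 90% power". Section 6.2 says the boundaries hold total type I error at or below 0.05.

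**The concern.** A weighted sum of two independent standard normal statistics is itself standard normal only if the squared weights add to 1. The printed weights add to 1, but their squares do not. The combined Z is therefore too narrow for the quantiles it is compared with, and the test rejects too rarely.

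This is the rule that decides the primary efficacy result. If it is programmed as printed, the 90% power and the boundary levels in section 6.2 are not what the trial delivers. A usual z between roughly 2.0 and 2.76 could also be significant under section 7.2 and not under 4.3, with nothing in the SAP saying which prevails. The dual programming in section 5.7 would not catch this, because both programmers would implement the same printed line.

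**Working it through.** **Inputs.** Rates 25% and 15%, 90% power, 670 evaluable, equal allocation (SAP 3.1, 3.3). Two-sided testing (protocol section 5: "All statistical tests of hypotheses will be two-sided"). Efficacy looks at about 350 and 620, final at 900 (SAP 6.1). Levels 0.00065, 0.0136 and 0.0457 (SAP 6.2). Protocol V3.0 enrolls 970.

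**The plan's own figures reproduce.** Pooled two-proportion formula without continuity correction:

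n per arm = [1.960 √(2 × 0.20 × 0.80) + 1.282 √(0.25 × 0.75 + 0.15 × 0.85)]² / 0.10² = 334.2, so 335 per arm and 670 in total, with power 0.901.

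All eight rows of the power table reproduce. Lan-DeMets O'Brien-Fleming spending, 0.025 per side, at 350/900, 620/900 and 1 gives 0.00065, 0.0136 and 0.0457. The sample size and boundaries are thus right for a standard normal statistic.

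**Spread of the printed Z.**

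- Final: w1 = 350/900 = 0.389, w2 = 550/900 = 0.611. Variance = 0.389² + 0.611² = 0.525; SD = 0.724.
- Second look: w1 = 350/620, w2 = 270/620; SD = 0.713.

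**True level at each look.**

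- Final, critical value 1.998: 1.998/0.7244 = 2.76, so the level is 2[1 − Φ(2.76)] = 0.0058, not 0.0457.
- Second look, critical value 2.468: 2.468/0.713 = 3.46, so the level is 0.0005, not 0.0136.
- The first look uses Z0,1 alone and is unaffected.

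**Power at the final look.** The expected full-sample z is 0.10 / √(2 × 0.20 × 0.80/335) = 3.236. Assume evaluable children are spread over the stages in proportion to enrollment.

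- Printed weights: mean of Z = 3.236 × (0.389 √0.389 + 0.611 √0.611) = 3.236 × 0.720 = 2.33. Power = Φ[(2.33 − 1.998)/0.724] = 0.677.
- Square-root weights: mean 3.236, SD 1. Power = Φ(3.236 − 1.998) = 0.892.

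**All three looks.** Simulation with 8 million trials per setting, SAP levels throughout, homogeneous effect and no enrichment for power. The 684 column adds the SAP's 2% sequential inflation (670 × 1.02).

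| Looks | Weights | Total type I error | Power, 670 evaluable | Power, 684 evaluable |
|---|---|---|---|---|
| 350/620/900 | printed | 0.0065 | 68.3% | 69.4% |
| 350/620/900 | square root | 0.0499 | 89.5% | 90.1% |
| 315/630/900 (35%/70%, the 4.3 simulation assumption) | printed | 0.0075 | 69.6% | 70.8% |
| 350/620/970 | printed | 0.0073 | 69.2% | 70.4% |
| 350/620/970 | square root | 0.0508 | 89.5% | 90.1% |

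Using the unpooled variance (expected z of 3.261) moves power at 350/620/900 with 670 evaluable from 0.68 to about 0.69.

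**The equivalence claim.** Without enrichment the usual z on all subjects is approximately √(n1/n) Z0,1 + √(n2/n) Z2. The sentence in 4.3 is therefore true of square-root weights and false of the printed ones.

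**The case against.** The best defense is that the formula is a misprint and the trial would not have been analyzed that way. Section 4.3 itself calls Z equivalent to the usual statistic and compares it with standard normal quantiles, which makes sense only with square roots. It also reports that its simulations showed little effect on power when the treatment effect is homogeneous, which does not fit a loss of about 22 points. Sections 7.2 and 7.2.1 and protocol 5.1 describe an ordinary stratified Mantel-Haenszel test; if that is run without enrichment, power stays near 90%. Section 4.3 words enrichment as optional. A radical or exponent could have been lost when the PDF was read. Finally, type I error of 0.7% still meets the promise of at most 0.05.

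Much of this is fair as to intent. The 68% applies only if the printed line is programmed, and false positives are not inflated. But the SAP does not say which formula its simulations used, and both SAP versions read the same, which weakens the PDF explanation without excluding it. Section 3.1 says the enrichment design will be used, and 4.3 applies the weighted statistic at every later look. If square roots or a plain Mantel-Haenszel test were meant, the text has to say so: choosing between rules after results are known would be a post hoc choice of primary test.

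**Conclusion.** The point holds and must be fixed. As printed, the combined statistic has SD 0.724 rather than 1 at the final analysis. Total two-sided type I error is 0.0065 to 0.0075 across the plausible look schedules. Power for 25% versus 15% at 670 evaluable is 68% to 70%, against the stated 90%.

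The power figures assume the formula is implemented literally, a homogeneous effect with no enrichment, the SAP's boundary levels, and evaluable subjects in proportion to enrollment. The type I figures do not depend on whether enrichment occurs, since under a global null Z2 is standard normal either way. The error is conservative, so the harm is lost power. Separately from the algebra, sections 4.3 and 7.2 name different primary tests: at the final look, the weighted rule and the ordinary test reject at rates of 0.677 and 0.892 under the design alternative.

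**What to change.** In section 4.3, replace the weights with √(n1/(n1+n2)) and √(n2/(n1+n2)) at the second interim and the final analysis, using planned values of n1 and n2 fixed in advance. State in section 7.2 that this combined statistic is the primary test if enrichment was triggered, and that otherwise the ordinary stratified Mantel-Haenszel statistic on all subjects is used. Extend section 7.2.1 to say how the stage combination and the imputation pooling fit together; its unit standard error is correct once square-root weights are used. Confirm which formula the section 4.3 simulations used, and rerun them if it was the printed one.

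At the same time, settle whether the weights and boundaries rest on 900 (SAP) or 970 (protocol V3.0). With looks at 350, 620 and 970, the same spending function gives levels of about 0.0004, 0.0100 and 0.0468.

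The weight correction is one line, with short matching edits in 7.2 and 7.2.1. It needs no extra patients or data, but should be made before unblinded results are seen.
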